4.1.5. Complicated peripheral arterial disease

Cases atherosclerosis peripheral arteries leading to the need for surgery (reconstructive vascular surgery, amputation, carotid endarterectomy, aorto-femoral bypass, etc.)

4.1.6. Coronary revascularization

Taking into account all the cases of revascularization procedures

5. COLLECTION AND ANALYSIS OF STATISTICAL DATA.

Statistical analysis was performed using a standard statistical package IBM SPSS Statistics Version 22 for Windows and MedCalc software version 18.3. It involves analysis of clinical predictors

- all cause mortality
- cardiovascular mortality
- all cardiovascular events
- stroke
- any, significant and major hemorrhage

For continuous variables will be analyzed and the distribution criteria for its compliance with the normal using the Kolmogorov-Smirnov test. To describe the features of the normal distribution using the mean with standard deviation

indication ($M \pm SD$). For signs with non-normal distribution when reporting the results indicate the median and interquartile range - the 25th and 75th percentiles ($Me (Q1-Q3)$). Discrete values are calculated as a percentage, the significance of differences were compared by Pearson criterion χ^2 . Comparison of quantitative traits obeying the normal distribution, is carried out using t-criterion Student, unnormal distribution - by using the non-parametric test, the Mann - Whitney and Kruskal - Wallis test for unrelated groups. For quantitative evaluation of the values calculated correlation coefficient is obtained and the accuracy depending on the Pearson's criteria (normal distribution) or Spearman (with a deviation from the normal distribution) for bilateral hypothesis testing criterion. The rating values of the predictor is conducted by plotting ROC curve and calculating the area under the curve (AUC). Treatment Evaluation of Frequency Allocations alleys and genotypes studied these genes will be performed using "Gene Expert" unified program. Genotype frequency distribution was calculated (the Hardy-Weinberg equilibrium test), genetic risk of NO using multiplicative general, dominant and recessive inheritance models. To assess the effect of clinical factors on the independence of the risk of adverse outcomes is performed using the Kaplan-Meier method using the log-rank test (Log Rank) and using Cox regression.

The regression analysis Univariate Cox included parameters are different when the comparative analysis between the groups of patients with a favorable and unfavorable outcome. The development of prognostic functions performed by using multivariate logistic regression. For all types of analysis were considered statistically significant value of $p < 0,05$.

It is supposed to analyze the prognostic data for specific groups of patients:

- patients 75 years and older
- patients with "early" debut atherosclerosis (men younger than 55 years, women younger than 60 years)
- patients with diabetes
- patients with CKD

7. ETHICAL AND LEGAL ASPECTS.

7.1 Informed consent of the patient.

Patients who meet all eligibility criteria, are considered suitable. Before inclusion in the clinical study of the patient must provide written consent to participate in the study, after the nature of the study will be explained verbally and in writing. Patients should be informed that in the course of study they will have taken blood for research purposes, including for genetic analysis.

7.2 The principle of confidentiality.

The data obtained from the study, and stored in the computer must be protected, as required by the law on personal data protection. The researchers will treat all personal information about the patient obtained during the investigation, in full respect of medical confidentiality and personal data protection law.

8. DATA OWNERSHIP AND USE OF RESEARCH RESULTS.

Each research group has the right to publish their own data, obtained as a result of the study.

Publication and other use of materials produced in other centers, with the consent of researchers, guiding the work of the centers.

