2. STUDY DESIGN AND PATIENT'S SELECTION

2.1. STUDY DESIGN

This is the Russian multicenter observational study of ACS patients with at least one-year follow-up. We planned to include 1700 ACS patients admitted to invasive hospitals. The follow-up will continue until at least 200 deaths for any reason.

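### Student's pooled-variance t-test on about 200 deaths versus 1500 survivors gives miscalibrated p-values for mean differences when spreads differ; naming Welch's test is a cheap, optional improvement

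*Combined protocol and SAP*

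**What the plan says.** Section 5 (Collection and analysis of statistical data) sorts continuous variables by a single check, "compliance with the normal using the Kolmogorov-Smirnov test". For those judged normal it says: "Comparison of quantitative traits obeying the normal distribution, is carried out using t-criterion Student". The rest go to Mann-Whitney or Kruskal-Wallis. Equality of variances, an unequal-variance version of the t-test and a test of spread are not mentioned.

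The same section says how the comparison is used. Univariate Cox regression "included parameters are different when the comparative analysis between the groups of patients with a favorable and unfavorable outcome". The significance threshold is 0.05 for every analysis. Prognostic functions are then built by multivariable logistic regression.

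The group sizes come from section 2.1: "We planned to include 1700 ACS patients admitted to invasive hospitals" and "The follow-up will continue until at least 200 deaths for any reason". The primary endpoint in section 4.1 is death from any cause.

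**The concern.** Student's t estimates one common variance from both groups. With equal group sizes, unequal spread hardly matters. With one patient who died for every 7.5 who survived, the pooled variance mostly reflects the survivors, whereas the true uncertainty of the difference comes mostly from the smaller group of deaths. If the deaths are more variable, the standard error is too small and the test rejects too often for equal means. If they are less variable, it rejects too rarely. The normality check looks at shape and is not designed to find this.

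What is at stake is the meaning of the p-values in the outcome-group comparison, and which traits are declared different in mean and sent on to univariate Cox regression.

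**Working it through.** **Inputs.**
- Group sizes: 200 deaths and 1700 − 200 = 1500 survivors (section 2.1; 200 is a minimum).
- Significance level 0.05 (section 5), taken as two-sided. Section 5 says "for bilateral hypothesis testing criterion" only for correlations, so this is an assumption for the t-test.
- SD ratio r = SD in deaths / SD in survivors. The documents give none; a range of 0.8 to 1.5 is assumed, with the survivors' SD set to 1.

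**Formulas (large-sample, equal means).**
- Pooled variance: sp² = (199·r² + 1499)/1698
- Variance that Student's t assumes for the difference: A = sp²·(1/200 + 1/1500) = sp²·0.0056667
- True variance of the difference: T = r²/200 + 1/1500
- Effective critical value: c = 1.96·√(A/T)
- Actual error rate: 2·(1 − Φ(c))

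**Step 1: reproduce the plan's 5%.** At r = 1, A = T = 0.0056667, so c = 1.96 and the rate is 5.0%. The stated level is reproduced under equal spread.

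**Step 2: vary the spread.**

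| r | sp² | A | T | c | Actual rate |
|---|---|---|---|---|---|
| 0.8 | 0.958 | 0.00543 | 0.00387 | 2.322 | 2.0% |
| 1.0 | 1.000 | 0.00567 | 0.00567 | 1.960 | 5.0% |
| 1.1 | 1.025 | 0.00581 | 0.00672 | 1.822 | 6.8% |
| 1.25 | 1.066 | 0.00604 | 0.00848 | 1.654 | 9.8% |
| 1.5 | 1.147 | 0.00650 | 0.01192 | 1.447 | 14.8% |

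The rate reaches 10% at r = 1.26. In 40,000 simulated data sets per ratio, Student's t gave 1.9%, 5.0%, 9.8% and 14.7% at r = 0.8, 1.0, 1.25 and 1.5. Welch's test stayed between 4.9% and 5.0% for r from 0.75 to 1.5.

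**Step 3: vary the split.** At 300 versus 1400 and r = 1.25, A = 0.00445 and T = 0.00592, so c = 1.699 and the rate is 8.9%. At 850 versus 850 it is 5.0%.

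**Step 4: does the normality check repair it?** With normal data and the Lilliefors form of Kolmogorov-Smirnov applied to the pooled sample (3000 data sets per ratio), the check flagged 5–6% of samples at r = 1.25 to 1.3 and 14% at r = 1.5. The whole rule (normality check, then t or Mann-Whitney) still rejected 9.5% at r = 1.25 and 13.8% at r = 1.5. For traits that are normal within groups, it does not.

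**Step 5: power for a true difference of 0.2 survivor SD.**
- r = 1.0: 0.2/√0.0056667 = 2.657, and Φ(2.657 − 1.960) = 76% for both tests.
- r = 0.8: 0.2/√0.00387 = 3.216. Welch: Φ(3.216 − 1.960) = 90%. Student: Φ(3.216 − 2.322) = 81%.
- r = 1.25: 0.2/√0.00848 = 2.172. Welch: Φ(2.172 − 1.960) = 58%. Student: Φ(2.172 − 1.654) = 70%. Allowing for simulation, about 59% versus 69%.

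**Step 6: carry the screen into Cox regression.** In simulations with a true difference of 0.2, the share of data sets significant at both stages was 80.0–80.6% for Student then Cox and 80.3–80.6% for Welch then Cox at r = 0.8. At r = 0.7 it was about 83% for both. One of these simulations assumed uniform death times, with survivors censored at the end. With equal means and r = 1.25, the share passing both stages fell from 9–10% with Student to 5–5.5% with Welch.

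**The case against.** The strongest reply is that the groups are formed by outcome. A trait wholly unrelated to death has the same distribution in deaths and survivors, hence the same SD, and Student's t keeps its 5%. Equal means with wider spread in deaths describes a trait that is related to death, with risk at both extremes. A reader might infer that the plan doubles the rate at which irrelevant predictors enter the model. The documents do not support that. The error concerns only the null hypothesis of equal means, and this reply stands in full.

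A reader might also infer that Welch's test would rescue predictors the plan loses. Step 6 shows otherwise. The gain of about 9 points at r = 0.8 is gone at the Cox stage, because the usual Cox and logistic tests respond to unequal spread much as Student's t does. This stands too.

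Third, many traits may never reach the t-test. At 1700 patients the Lilliefors form rejects normality in 87.5% of samples at a skewness of 0.3, though the standard form rejects only 20%. The plan does not say which form is used, or whether it is applied to pooled or separate groups. This narrows the point without removing it.

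Finally, the SD ratios are assumed and 200 deaths is a minimum. Both are true. They limit what can be said about size, not the direction of the effect.

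**Conclusion.** The point holds in a limited form. The plan names a pooled-variance test for an outcome comparison of about 1 to 7.5 and checks only normality. Its p-values for mean differences are therefore correct only if spreads are equal. The departure is modest at a ratio of 1.1 and about a doubling at 1.25, on assumed ratios and with about 200 deaths; it shrinks as the split becomes more even. Nothing in the documents shows that spreads do differ. Only traits passing the normality check are concerned. The primary endpoint, the Kaplan-Meier analysis and the Cox estimates themselves are not affected.

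What the change buys is valid p-values for differences in means and fewer traits called different in mean because of spread alone. Minor; an optional improvement.

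**What to change.** In section 5, replace the reference to Student's t with: *Welch's (unequal-variance) t-test for two-group comparisons of means, with no preliminary test of variances*.

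The cost is one phrase. It needs no new data, and there is no material power loss when spreads are equal. One small downside should be accepted knowingly: traits with wider spread in deaths will pass the screen less often, as the r = 1.25 line of step 5 shows. The change should not be presented as increasing the number of predictors found significant in Cox or logistic regression.

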1. THE AIM OF THE STUDY

To develop a model of individualized risk of coronary heart disease outcomes and side effects of therapy based on clinical and instrumental, biochemical, and genetic parameters in patients with ACS.

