4. ENDPOINTS

4.1. The primary endpoint

- Dearth from any causes

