5.2. Secondary end-points

1. cardiovascular (atherothrombotic) events (cardiovascular death, non-fatal myocardial infarction, non-fatal stroke)
2. non-fatal myocardial infarction
3. recurrent acute coronary syndrome (all cases of recurrent myocardial infarction or unstable angina after the index events)
4. recurrent PCI (all cases of recurrent PCI after the index hospitalization)
5. complicated atherosclerosis
6. non-fatal stroke

5.3 Other Pre-specified Outcome Measures:

1. Bleeding

all cases of bleeding during and after the index hospitalization

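### Kaplan-Meier is the only survival-curve method named for outcomes that death can preclude, so event risks read from it would be somewhat too high

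*Combined protocol and SAP*

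**What the plan says.** The aim (section 1) is "To develop a model of individualized risk of coronary heart disease outcomes and side effects of therapy". The primary endpoint (section 4.1) is "Dearth from any causes". The secondary endpoints in section 5.2 include the composite "cardiovascular (atherothrombotic) events (cardiovascular death, non-fatal myocardial infarction, non-fatal stroke"), and bleeding is a further pre-specified outcome in section 5.3.

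Section 5 (Collection and analysis of statistical data) lists the outcomes whose predictors will be analysed: all-cause mortality, cardiovascular mortality, all cardiovascular events, stroke, and "any, significant and major hemorrhage". Three statements there matter for this point:

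- The purpose of the survival methods is given as "To assess the effect of clinical factors on the independence of the risk of adverse outcomes".
- The methods are "performed using the Kaplan-Meier method using the log-rank test (Log Rank) and using Cox regression". The sentence does not separate one outcome from another.
- The individual risk functions use a different method: "The development of prognostic functions performed by using multivariate logistic regression".

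Prognostic analyses are also planned in four groups, among them "patients 75 years and older" and patients with CKD. The document does not mention cumulative incidence, competing events or a censoring rule.

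**The concern.** A patient who dies of cancer can no longer have a stroke or a bleed. Kaplan-Meier and ordinary Cox regression have no place for that death except as a censored observation. The curve then treats the dead patient as someone who could still have had the event later, and 1 minus Kaplan-Meier describes a population in which nobody dies of anything else. It is not the proportion of patients who will have the event.

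Absolute risk is central to a study that wants to weigh coronary outcomes against side effects of therapy in the individual patient. Because the excess grows with competing mortality, it would also differ between groups with different mortality and so distort side-by-side comparisons of their event curves.

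**Working it through.** **Is there a figure to reproduce?** The plan gives no event rates and no expected risks for stroke, haemorrhage or cardiovascular events. The only usable inputs are in section 2.1: 1700 patients, and follow-up until at least 200 deaths. These give a crude mortality of 200/1700 = 11.8%.

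**Which outcomes are exposed?**

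- All-cause death: not exposed, since nothing competes with it.
- Stroke and haemorrhage: exposed to deaths that occur before any such event. Whether a fatal stroke or fatal bleed is an event or a competing death depends on whether the outcome includes fatal cases.
- Cardiovascular mortality: section 4.1.3 limits this label to deaths from myocardial infarction, CABG and sudden cardiac death. Deaths from stroke, major bleeding, pulmonary embolism and operation go into a separate category and therefore compete with it, as do non-cardiovascular deaths.
- Cardiovascular events: exposed only to deaths outside the composite's own cardiovascular-death component.

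**Direction.** Let h1(u) be the event hazard, and let S1(u) and S2(u) be the survival functions built from the event hazard and the competing-death hazard. Then 1 minus Kaplan-Meier estimates ∫h1·S1 du, while the true cumulative incidence is ∫h1·S1·S2 du. As S2 is at most 1, the first can never be smaller than the second.

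**Size.** Assume constant hazards over one horizon. Let K be the risk read from 1 minus Kaplan-Meier and D the competing-death risk over the same horizon:

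- λ1 = −ln(1−K), λ2 = −ln(1−D)
- cumulative incidence C = λ1/(λ1+λ2) × [1 − exp(−(λ1+λ2))]
- relative excess = K/C − 1

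Example with K = 10% and D = 11.8%: λ1 = 0.1054, λ2 = 0.1252, sum 0.2305. C = (0.1054/0.2305) × (1 − 0.9 × 0.8824) = 0.457 × 0.2059 = 9.41%. The excess is 0.59 points, or 6.3% relative.

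| D | Source of D | C when K = 3% | C when K = 5% | C when K = 10% | Relative excess |
|---|---|---|---|---|---|
| 5.9% | half of the 200 deaths compete (assumption) | 2.91% | 4.85% | 9.71% | about 3% |
| 11.8% | all 200 of 1700 compete | 2.82% | 4.70% | 9.41% | about 6% |
| 25% | assumed subgroup mortality | 2.61% | 4.35% | 8.71% | about 15% |
| 40% | assumed subgroup mortality | 2.35% | 3.92% | 7.87% | about 27% |

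The values of K are also assumptions, chosen to span plausible event risks.

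**The case against.** The strongest reply is that the plan does not use Kaplan-Meier or Cox to produce the individual risks. Several parts of it stand.

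- **The prognostic functions are logistic.** A reader might infer from the stated aim that each patient's predicted risk will be inflated. The documents do not support that. Logistic regression counts a patient who dies of another cause as a non-event, so it does not carry this bias. Its weaknesses are different: no prediction horizon is stated, and follow-up length varies.
- **The survival methods are there to assess factor effects.** A reader might infer that the Cox and log-rank results are invalid. They are not. With competing deaths censored, Cox regression estimates a cause-specific hazard ratio and the log-rank test compares cause-specific hazards.
- **Censoring at death is not stated.** It is implied by the methods named. Strictly, the plan is silent.
- **Elderly and CKD patients.** A reader might conclude that risks in these groups are overstated by a known, large amount. The direction is plausible if their competing mortality is higher, but the documents give no mortality for any subgroup.
- **The 11.8% is not a planned mortality at a horizon.** It comes from a stopping rule with variable follow-up. Deaths that follow the event, or that are part of the outcome, do not compete, so treating all 200 as competing is a high assumption for that count. In the other direction, the rule says at least 200, so the final count may be larger.

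The reply does not remove the point. Kaplan-Meier remains the only method named for showing event occurrence over time, and the plan nowhere says that its curves will be confined to all-cause death. A Kaplan-Meier risk and a logistic risk for the same outcome could then disagree for this reason alone.

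**Conclusion.** The point holds in a limited form. For stroke, haemorrhage, cardiovascular mortality and cardiovascular events, the plan names no method that handles death from other causes and gives no rule for it. Any event risk read from 1 minus Kaplan-Meier for these outcomes would be too high. For the whole cohort the effect is modest: about 6% relative as an upper figure at 200 deaths in 1700, and about half of that if half the deaths compete. It could be material in a high-mortality subgroup, but the sizes given for 25% and 40% mortality are illustrations. All sizes assume constant hazards; the direction does not.

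The primary endpoint, the hazard ratios, the log-rank tests and the logistic prognostic functions are outside this criticism. It is a cheap improvement to the plan and does not threaten the study's main conclusion.

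**What to change.** Amend section 5 as follows:

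1. Keep Kaplan-Meier, log-rank and Cox for all-cause death.
2. For every other outcome, define which deaths are part of the outcome and which compete, in line with the categories in section 4.1.3. Show Aalen-Johansen cumulative incidence with death outside that outcome as the competing event.
3. Keep Cox and log-rank for factor effects on these outcomes, and label the results as cause-specific.
4. Give the logistic prognostic functions a fixed horizon and check their predicted risks against cumulative incidence at that horizon.

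The cost is a few sentences and modest extra programming, possibly in a package beyond the two named in section 5. No new procedures are needed: section 4.1.3 already classifies cause of death, and the planned survival analysis of all-cause death already requires dates of death. Reported event risks will be slightly lower than Kaplan-Meier would have shown.

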In the previous part of the study, the sample of patients of Moscow, St. Petersburg, Kazan, Chelyabinsk, Stavropol, Perm, and Rostov-on-the-Don was formed, of 1,200 people admitted due to acute coronary syndrome (ACS) including unstable angina and acute myocardial infarction, at coronary care units with follow-up for three years. We found several factors, including genetic, that significantly affect the outcomes of the disease. Coronary atherosclerosis and its complications now considered as a multifactorial disease associated with inherent factors. Therefore, the project provides, besides accounting a significant amount of clinical and instrumental data, the determination of a wide range of genotypes and alleles of polymorphic markers candidate genes encoding the protein factors of the hemostatic system, enzymes of lipid metabolism system, and anti-inflammatory cytokines. It is assumed that the prediction outcomes of coronary heart disease should be carried out taking into account the fact that several factors (gender, diabetes, age, aortic stenosis, atrial fibrillation, etc.) can not only significantly change the forecast itself but also affecting the significance of other risk factors. Since the last study, the standards significantly of ACS management changed. Invasive treatment not only creates opportunities to reduce coronary mortality but also increased demands on the patient's adherence to the assigned medication and creates additional risks associated with its activity (especially with an antithrombotic treatment activity). In these circumstances, the development of personalized approaches to prescribing drugs is particularly important. Thus, the prediction of coronary heart disease outcomes after an ACS on a set of clinical, instrumental, biochemical and genetic indicators is of great importance, as it allows to plan the most optimal treatment for the individual patient.

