3. STUDY PROCEDURES

3.1. THE SEQUENCE OF STUDY

Stationary Phase

1st day:

Symptoms of acute coronary syndrome, leading the patient to the hospital
Conformity assessment criteria for inclusion in the study

Written informed consent

blood samples for genetic analysis

Filling Case Report Form (CRF)

2nd - 5th day

Filling in the missing information in the CRF

During the CAG or PCI is an extensive video research and filled with a separate PCI card

Upon cancellation of the CAG and PCI card is filled with the count of "rejection reason "

Register endpoint - filling in the relevant sections of the CRF
discharge planning

6th day - discharge from the hospital

Echocardiography - attached full movie, and is filled with a special card echocardiogram

Final inspection and afterfilling CRF

Talk with the patient follow-up plan

The introduction of information into an electronic database

Sending information to the Coordination Center for Research

Outpatient treatment stage

25 ± 5 days from the date of inclusion (but no earlier than 5 days after discharge)

Telephone contact with the patient or his relatives

Register endpoint and adherence to treatment - filling in the relevant sections of the CRF

90 ± 15 days from the date of inclusion

Telephone contact with the patient or his relatives

Register endpoint and adherence to treatment - filling in the relevant sections of the CRF

180 ± 15 days from the date of inclusion

control monitoring visit

ECG

Register endpoint and adherence to treatment - filling in the relevant sections of the CRF.

365 ± 15 days from the date of inclusion

Telephone contact with the patient or his relatives.

Register endpoint and adherence to treatment - filling in the relevant sections of the CRF

Next phone contacts 1 time in 6 months to achieve thereof, the observation of the last patient included in the study (or up to 200 deaths, if for the planned observation period their number was less).

The final filling of card and electronic form, sending the information to the coordination center.

Appropriate CRFs and forms for the events should be completed in accordance with the instructions in the manual of the researcher.

In the case report of the patient information is recorded on the adverse clinical outcomes that have developed since the last contact with the patient (see. the relevant section of the CRF). Also recorded group of drugs, which the patient took over this time period.

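### The prognostic function is assigned to logistic regression with no prediction horizon while follow-up is open-ended, so a predicted absolute risk has no defined period if the outcome is coded at study close

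*Combined protocol and SAP*

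**What the plan says.** Section 1 gives the aim: "To develop a model of individualized risk of coronary heart disease outcomes and side effects of therapy". The Introduction says why such prediction is wanted: "it allows to plan the most optimal treatment for the individual patient".

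Section 5 (Collection and analysis of statistical data) names one method for this aim: "The development of prognostic functions performed by using multivariate logistic regression". The same section plans ROC curves with AUC. It also plans Kaplan-Meier, log-rank and Cox analyses, but assigns these to the independent effect of clinical factors and to univariate screening, not to the prognostic function.

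Section 2.1 describes 1700 patients "with at least one-year follow-up" and adds: "The follow-up will continue until at least 200 deaths for any reason". Section 3.1 schedules a contact at "365 ± 15 days from the date of inclusion", and after that: "Next phone contacts 1 time in 6 months to achieve thereof, the observation of the last patient included in the study". A bracketed clause in the same section then lengthens follow-up where deaths are too few: "or up to 200 deaths, if for the planned observation period their number was less".

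No prediction period is stated in the aim, the endpoint sections (4.1, 5.2, 5.3), the ROC/AUC text or the logistic regression sentence. The three-year follow-up in the Introduction belongs to the previous part of the study.

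**The concern.** A logistic model gives the probability that a yes/no outcome occurs within whatever window was used to code it. If the window is the same for everyone and is stated, the probability has a plain meaning. If the outcome is coded as having occurred by study close, a patient enrolled early has a longer window than one enrolled late. Even if all patients enrol together, the window is set by the closing date, which can depend on when the 200th death occurs.

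The resulting number would then mix follow-up lengths, or carry a length nobody chose. A clinician told that a patient's risk is 12% could not say whether that covers one year or three. An AUC computed on the same coding has no stated period either. This matters because the study wants individualised risk in order to plan treatment.

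**Working it through.** **Step 1: does the text supply a horizon?** Taken together, the sections give a minimum follow-up of one year, no maximum, a study-wide close and an extension driven by deaths. The day-365 contact is one of several scheduled contacts and is not named as the prediction time. A horizon is therefore not stated, and coding at close is not excluded.

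**Step 2: what can be computed from the documents alone?** With 1700 patients and exactly 200 deaths, the crude proportion at close is 200/1700 = 11.8%. The plan gives no accrual period, closing date, event rate or loss rate, so it has no figure of its own to reproduce. Everything below is assumed, for illustration only.

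**Step 3: model.** Accrual is uniform over A years, with no loss. The study closes d years after the last patient reaches one year, so follow-up is uniform on [1+d, 1+A+d]. Death follows a Weibull distribution with risk F(t) = 1 − exp(−(λt)^k). Solve λ so that the average of F over the follow-up range equals 200/1700, then read off the one-year risk F(1) and the time at which F(t) = 11.8%.

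Worked case, k = 1, A = 2, d = 0: 1 − [exp(−λ) − exp(−3λ)]/(2λ) = 0.1176 gives λ = 0.0629 per year. One-year risk = 1 − exp(−0.0629) = 6.1%; three-year risk = 1 − exp(−0.1887) = 17.2%. Patients with these two follow-up lengths are coded on the same yes/no scale, and the model averages 11.8%.

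| Accrual A (years) | Delay d (years) | Shape k | True 1-year risk | Time at which risk is 11.8% (years) | Deaths within 1 year |
|---|---|---|---|---|---|
| 1–3 | 0 | 0.5–1.0 | 4.92–9.76% | 1.48–2.48 | 84–166 |
| 1–3 | 0 | 0.2–0.4 | 8.45–10.93% | 1.48–2.40 | 144–186 |
| 1–3 | 0.5–2 | 0.5–1.0 | 2.75–8.49% | 1.99–4.49 | 47–144 |
| 0.05 | 0 | 0.5–1.0 | 11.5–11.6% | 1.02–1.03 | 195–198 |
| 0.05 | 0.5–2 | 0.5–1.0 | 4.05–9.64% | 1.5–3.0 | 69–164 |

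Very fast accrual removes the problem only if the study also closes at one year. Strongly front-loaded mortality (small k) shrinks it: with d = 0 the smallest gap in the second row is 11.76 − 10.93 = 0.83 percentage points.

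**Step 4: relative effects and ranking.** Take a binary predictor with prevalence 50%, a true hazard ratio of 1.5 and an overall risk of 11.76%. Solving p0 + 1 − (1 − p0)^1.5 = 2 × 0.1176 gives p0 = 0.0955 and p1 = 0.1398. The odds ratio is (0.1398/0.8602)/(0.0955/0.9045) = 1.54. Integrating over the unequal follow-up gives 1.534 to 1.544 (prevalence 20% or 50%, shape 0.5 or 1.0). In simulation (2,000,000 patients per scenario, normal log-hazard score with SD 0.7 or 1.0), the pooled AUC was 0.696–0.700 against a one-year AUC of 0.690–0.697 for SD 0.7, and 0.765–0.767 against 0.762–0.767 for SD 1.0. The differences were 0.001 to 0.007. These results assume that the predictor is unrelated to enrolment date and to loss to follow-up; nothing in the protocol indicates otherwise.

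**The case against.** The logistic regression sentence only names a method. It does not say that the outcome is status at close. The design guarantees a one-year minimum and schedules endpoint registration near day 365, so logistic regression on one-year status fits the text and would be valid. This stands. A reader might infer that the plan commits itself to pooling unequal follow-up, or that logistic regression is wrong in itself; the documents support neither. What remains is that the text equally allows coding at close, and that following patients to 200 deaths suggests later deaths are meant to count.

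Time-to-event methods are already planned, so associations are handled with allowance for follow-up. That also stands, and it makes the repair cheap. It does not give the prognostic function a horizon.

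The function may be meant as a score, not a probability, and then the harm is small. The protocol does not say which. Individualised risk used to plan treatment points toward a probability but does not settle it.

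The closing rule in section 3.1 is awkwardly worded and no accrual period is given, so the spread of follow-up is unknown. This limits any statement of size. It does not remove the open-ended follow-up, which section 2.1 states separately.

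**Conclusion.** The point holds in a limited form. The prognostic function has no stated horizon, and follow-up has a minimum but no fixed end. If the outcome is coded at close, the absolute level of a predicted risk reflects accrual and closing date and covers no defined period. The evidence for this is the text, not the illustration.

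A reader might go on to infer that predicted risks will be wrong by a known, severalfold amount. The documents do not support that: the gap between 11.8% and the true one-year risk rests wholly on assumed accrual, close and hazard shape, and runs in the table from under one percentage point to about nine (11.76 − 2.75 = 9.01). Nor does the point undermine the choice of predictors or the ranking of patients, which barely change under the assumptions in step 4.

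It should still be fixed, because it touches the study's stated aim and the better-defined analysis uses data already planned.

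**What to change.** Replace the logistic regression sentence in section 5 with:

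> Prognostic functions will predict risk at 1 year from inclusion (and later stated horizons as follow-up allows). For all-cause death they will be developed by multivariable Cox regression with survivors censored at last contact, and predicted risk and AUC will be reported at that horizon. For non-fatal and cause-specific outcomes (cardiovascular death, cardiovascular events, stroke, bleeding), death from other causes will be treated as a competing event when absolute risk is reported.

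The last sentence is needed because turning a Cox model that censors deaths into a probability overstates absolute risk for those outcomes.

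An acceptable alternative keeps logistic regression with the outcome defined as event status by one year, using the day 365 ± 15 contact. Patients who die earlier without the event count as non-events, and a rule is stated for patients lost earlier.

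No new data are needed. The cost is modest extra analysis work and a check that the named packages provide a fixed-time AUC and competing-risk estimates. The logistic alternative also uses fewer deaths. Taking the standard-error ratio as roughly √(200/deaths within one year), 84 to 166 deaths (first table row) give standard errors about 55% to 10% larger, and 47 deaths (the lowest value in the third row) about 107% larger. With front-loaded mortality (144 to 186 deaths) the loss is about 18% to 4%.
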